b. Screen for Child Anxiety Related Emotional Disorders – Parent Version (SCARED-P)^{132,133}. Parent ratings represent important additional outcomes in all youth anxiety randomized trials^{136,137}. There is scant controlled parent data following youth participation in ABMT. We will address this gap in the literature by assessing outcome from parents' perspectives using the parent version of the SCARED. The reliability and validity of the SCARED-P have been demonstrated repeatedly and mirror those of the SCARED-C^{132,133,135}.

III. Potential Mediators and Moderator

We will assess each of the potential mediators and the hypothesized moderator shown in Figure 2 at each assessment session (Figure 3) to inform decisions about our future R01.

a. Attention Bias to Threat. As in prior research^{36,41}, attention bias to threat will be assessed with a probe-detection task identical to the one used in the PC Task, with the exception that unique faces will appear in this task (i.e., a different set of 10 faces will be used). Inaccurate responses when the probe appears on one side of the screen but patients select the other side will be excluded, as will trials with response latencies <50ms and >1200ms. Similar criteria have led to the exclusion of <5% of trials among adults³⁷ and children^{36,42}.

Attention bias scores will be calculated by subtracting the mean response time on trials in which the probe appears at the neutral face location from the mean response time on trials in which the probe appears at the angry face location. Only the 120 trials that present angry-neutral face pairs will be used to calculate scores (the 40 neutral-neutral trials will be excluded). Positive values reflect an attention bias towards angry faces.

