described earlier, reduction in attention bias toward threat and threat-related interpretation bias represent proposed potential mediators of ABMT^{61,62}, and [attention control is expected to moderate the effects of ABMT on anxiety symptom severity⁵⁵⁻⁵⁸.] Although it is premature given the current state of the field to pursue tests for the full moderated mediation chain depicted in Figure 2 in this R34, it is reasonable to use the data to gain some perspectives on the viability of proposed moderator and mediators so as to inform decisions to pursue them in the larger R01. [The traditional moderation analysis relies on least squares regression with a focus on the statistical significance of the product term of the independent variable (condition) and the moderator (attention control) in predicting the dependent variable (anxiety symptom severity)¹⁵³. In this R34 pilot study, and given our desire to balance risk of Type I and Type II errors, we will only test attention control as a moderator of the association between condition and anxiety symptom severity. The other two moderation effects depicted in Figure 2 will be tested in a larger R01 if initial support for the primary moderation hypothesis is obtained in this R34.

Mediation paths (Figure 2) can be explored in several ways. One strategy tests the joint significance of the path from the treatment to the mediator and the path from the mediator to the outcome. This follows the logic of the joint significance test of mediation by MacKinnon¹⁵⁴, but we will use the newer, more powerful partial posterior p value method by Biesanz¹⁵⁵. This latter approach fares better than the asymmetric confidence interval approach for testing statistical significance¹⁵⁵. A robust analog to the joint significance test will use Theil-Senn regression as applied to the target paths and then apply the logic of MacKinnon's joint significance to them. The magnitude of each indirect effect can be subjected to decompositional analyses through multiplicative and summation rules for mediation and the proportion of the total effect that each mediator accounts for can be documented (using the algorithms from the Mplus computer package¹⁵⁶). Confidence intervals around these decomposed effects can be formed using percentile bootstrapping, which perform better than bias-corrected bootstraps in the context of such mediation analysis – see Biesanz¹⁵⁵.]

Statistical Power

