Approaches to increasing statistical power in randomized clinical trials generally focus on increasing sample size, but an alternative strategy is to introduce covariates that reduce within-subject error and thereby increase the precision of estimated between-group differences. The latter approach leads to a more sensitive significance test for the treatment effect¹⁵⁷. In the proposed R34, our sample size will be constrained by the number of youth who do not respond to CBT in the current R01 MH079943 study. Thus, we will increase the statistical power available by adjusting for relevant covariates measured at pre. Covariate adjustment for the pre score on each outcome measure will substantially increase statistical power¹⁵⁸. For example, if pre and post scores correlate at $r=.65$ (which seems reasonable based on the test-retest reliability estimates for our outcome measures and preliminary pre to post data from R01 MH079943), then power of 0.80 to detect a mean difference of $d=.50$ is available with a sample size of approximately 36 per group. Our projected sample size of 35 per group maps closely onto this estimate. To increase statistical power further, we will covary [pre attention bias scores] and examine other characteristics measured at pre (e.g., age, gender, diagnosis, R01 MH079943 condition, past treatment, current medication use, number of comorbid diagnoses) to determine whether they differ across conditions. If they vary across conditions, we will include them as covariates which will reduce the "noise" in the estimated treatment effect and thereby increase power. In general, the robust methods of analysis will be as powerful or more powerful than the least squares regression methods, so the power estimates above apply, conservatively, to the robust methods of analysis as well.

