[For a test of moderation in Aim 3 that uses multiple regression, we will have power $> .80$ for a two tailed test ($\alpha=0.05$) of the interaction term based on an N of 70 for a medium effect size ($f^2=.15$).] For tests of mediation in Aim 3 that use bivariate or multiple regression, we will have power of about 0.80 for a two tailed test ($\alpha=0.05$) of a bivariate coefficient based on an N of 70 (i.e., pooling treatment & control groups) for an effect size that represents 10% explained variance, which seems reasonable for a mediator that is assumed to be relatively influential. For a multiple regression with two predictors, a two tailed test ($\alpha=0.05$), and an overall squared R of 0.20, the power is 0.80 to detect a coefficient that represents 10% unique explained variance. These levels of power seem reasonable given the preliminary nature of this facet of the research and the presumed role of the moderator and mediators based on substantive considerations.

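### Do the powers of about 0.80 given for the Aim 3 mediation tests overstate the chance of detecting a mediator?

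*Combined protocol and SAP*

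**What the plan says.** The last paragraph of Statistical Power covers Aim 3. It begins the mediation part with "For tests of mediation in Aim 3 that use bivariate or multiple regression, we will have power of about 0.80". After giving the two-sided 0.05 level, the sentence says what that power refers to: "of a bivariate coefficient based on an N of 70", at an effect of 10% explained variance. For a regression with two predictors and an overall squared R of 0.20, it adds that "the power is 0.80 to detect a coefficient that represents 10% unique explained variance". No power for an indirect effect is given.

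The tests are described in Data Analysis, Aim 3. "One strategy tests the joint significance of the path from the treatment to the mediator and the path from the mediator to the outcome". The plan presents this as the logic it starts from, "but we will use the newer, more powerful partial posterior p value method". Joint significance returns for the robust version: "A robust analog to the joint significance test will use Theil-Senn regression". The same section calls Aim 3 exploratory, as groundwork for a larger grant.

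Two statements bear on covariates. Statistical Power says "Covariate adjustment for the pre score on each outcome measure will substantially increase statistical power", and adds that pre attention bias scores will be covaried. Measures, under Potential Mediators and Moderator, says "We will assess each of the potential mediators and the hypothesized moderator shown in Figure 2 at each assessment session", so pre scores will exist for the mediators as well. Neither statement says whether the mediation regressions will contain them.

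**The concern.** The two powers are introduced as being for tests of mediation, and they are the only ones offered. The paragraph then concludes that these levels are reasonable for the mediators. But one significant coefficient does not establish mediation. If both paths must be significant, and each has power near 0.80, the power for the pair is roughly the product of the two, clearly below 0.80.

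A reader who carried 0.80 over to the indirect effect would expect to miss a true mediator about one time in five. On the two-path calculation with 10% on each path, the miss rate is 35-37% at N=70 and 42-44% with 63 completers. Aim 3 exists to decide which variables to pursue in a later trial, so a null result read as if power were 0.80 could lead to a useful mediator being dropped too readily.

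**Working it through.** **Inputs.** From Statistical Power: N=70, two-sided alpha 0.05, 10% explained variance for a bivariate coefficient, and 10% unique variance with overall R² = 0.20 for two predictors. From Preliminary Studies and Participants: 63 completers, range 60-66. From Statistical Power: d=1.16 for reduction in attention bias (adult clinical samples) and an assumed pre-post correlation of 0.65 for outcomes.

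**Formula.** Test of one coefficient with k predictors: noncentral F with 1 and N−k−1 degrees of freedom. The effect size is f² = (unique share)/(residual share). The noncentrality is λ = f²·N, or under the other common convention f²·(N−k−1). Results are given as first convention / second convention.

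**Step 1: the plan's own figures, N=70.**
- Bivariate: f² = 0.10/0.90 = 0.111, k=1. Power 0.785 / 0.773.
- Two predictors: f² = 0.10/0.80 = 0.125, k=2. Power 0.830 / 0.814.

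Both agree with the stated values to within about 0.03. Neither printed figure is wrong.

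**Step 2: both paths significant, 10% on each, no baseline covariates.** Condition is taken as the second predictor in the outcome model.

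| N | treatment to mediator | mediator to outcome | product |
|---|---|---|---|
| 70 | 0.785 / 0.773 | 0.830 / 0.814 | 0.652 / 0.629 |
| 63 | 0.740 / 0.727 | 0.788 / 0.769 | 0.584 / 0.558 |

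A simulation of 60,000 trials gave 0.631 at N=70 and 0.562 at N=63. Across 60-66 completers the product runs from 0.53 to 0.61. A product of 0.80 would need N of about 90-93. So the arithmetic behind the worry is sound.

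**Step 3: vary the treatment-to-mediator path.** The plan gives one estimate for it, d=1.16 for attention bias. Read as a between-group difference with equal arms, R² = 1.16²/(1.16² + 4) = 1.3456/5.3456 = 0.252, so f² = 0.252/0.748 = 0.336. Power for this path at N=70 is 0.998 / 0.997. With the mediator-to-outcome path unchanged:
- N=70: 0.998 × 0.830 = 0.83; 0.997 × 0.814 = 0.81.
- N=63: 0.995 × 0.788 = 0.78; 0.994 × 0.769 = 0.76.

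**Step 4: vary the covariates (10% on each path).** Add the outcome's pre score at r=0.65, which explains 0.65² = 0.4225, and keep the 10% shares as shares of total variance.
- Residual 1 − 0.20 − 0.4225 = 0.3775: mediator-to-outcome power 0.989 / 0.985, product 0.776 / 0.761 at N=70.
- Residual 0.80 × (1 − 0.4225) = 0.462: product 0.761 / 0.743 at N=70.

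Together these give 0.74-0.78 at N=70; the same steps give 0.68-0.73 at N=63. Adding the mediator's own pre score to its model, with an assumed correlation of 0.3 to 0.65 (the documents give none), takes the range to 0.78-0.95 at N=70. If the 10% shares instead refer to variance left after adjustment, nothing is gained: 0.62-0.65 at N=70.

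**Step 5: the test itself.** All of the above are least-squares F tests. The plan names the partial posterior p value method as the one to be used, and its power was not computed. Joint significance is kept for Theil-Sen regression, which was not computed either.

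**The case for a change.** The best case for a change runs as follows. Mediation is by definition a two-path claim, and the plan says so when it describes joint significance. Putting per-coefficient powers under a mediation label and then calling them reasonable invites the wrong inference. The shortfall is also not peculiar to joint significance: for the percentile bootstrap intervals that the plan intends for indirect effects, a simulation at the same effect sizes without baseline covariates (3,000 trials) had the interval exclude zero in 0.63 of trials at N=70 and 0.55 at N=63. The adult d=1.16 may not carry over to this sample, as the plan admits, and it says nothing about interpretation bias. A clarifying sentence costs almost nothing.

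Most of that stands as description. The plan gives no indirect-effect power, and for a mediator with 10% on both paths and no pre scores the two-path power is below 0.80. What does not stand is the step from there to a defect. The plan offers 10% as the size of one coefficient and does not describe a mediator with 10% on both paths. Leaving out baseline scores is a doubtful default when the same section plans to adjust for outcome pre scores and pre attention bias. The 63 completers are those who reach follow-up, whereas Aim 3 is also analysed at posttreatment, and multiple imputation and intent-to-treat analyses are planned. A single replacement figure would therefore rest on more assumptions than the figures now printed.

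**Conclusion.** No change is needed. Both stated powers are correct and labelled as power for one coefficient. Indirect-effect power is a missing detail, and supplying it would bring no practical gain.

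With 10% on both paths and no baseline covariates, joint-significance power is about 0.63-0.65 at N=70 and 0.56-0.58 at N=63. It is about 0.81-0.83 and 0.76-0.78 if the attention-bias path matches d=1.16, assuming that value is a between-group effect and transfers from adults. Pre-score adjustment could raise it or leave it unchanged, depending on how the 10% shares are defined. The power of the named mediation test is unknown from the documents.

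No primary or secondary hypothesis, sample size, data collection or analysis depends on the answer. Aim 3 is exploratory, and the plan already justifies its power by the preliminary nature of that work. An analyst reporting Aim 3 can note that the planned powers were per path and read a null mediation result with that in mind.
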